## 6.2.2.2. Radiographic

For patients who elect to participate in optional CT scans, a non-contrast low-dose kidney-protocol CT scan will be performed at baseline (may be performed up to 3 days prior to Day 1), and at Month 15.

For patients who elect to participate in optional CT scans and terminate the study early, a CT scan should be performed at the ET visit only if this visit occurs after Month 6 and at the discretion of the Investigator, and where permitted, following consultation with the Medical Monitor. Optional CT scans will be analyzed centrally.

#### **6.2.3.** Estimated Glomerular Filtration Rate

Blood samples for the assessment of eGFR (mL/min/1.73m^2) will be obtained at the time points specified in the Schedule of Assessment (Table 1).

eGFR will be calculated based on the CKD-EPI formula (see Section 10.1).[Levey 2009; Schwartz 2009]

## 6.3. Pharmacodynamic Assessments

Urine and blood samples will be collected for assessment of PD parameters (plasma oxalate and plasma glycolate, and 24-hour urinary glycolate) at the time points specified in the Schedule of Assessments (Table 1). On dosing days, all blood and urine samples will be collected prior to study drug administration.

All PD assessments will be analyzed centrally. Postdose PD results will not be distributed to the sites until after the last patient completes assessments at the Month 15 visit. Site personnel should refrain from obtaining or viewing local oxalate, calcium oxalate supersaturation, or glycolate assessments, except as medically indicated, due to risk of unblinding (Section 3.5). Details regarding the processing and aliquoting of PD samples for shipping and storage are provided in the Laboratory Manual.

Where local regulations allow and infrastructure is in place, a healthcare professional may collect urine or blood samples offsite.

#### 6.4. Pharmacokinetic Assessments

Blood samples will be collected for the assessment of lumasiran PK parameters at the time points indicated in the Schedule of Assessments (Table 1). A detailed schedule of time points for the collection of blood samples for PK analysis is in Table 2.

The concentration of lumasiran in blood samples will be determined using a validated assay. Details regarding sample volumes to be collected, and the processing and shipping of the samples will be provided in the Laboratory Manual.

## 6.5. Safety Assessments

The assessment of safety during the study will consist of the surveillance and recording of AEs including SAEs, recording of concomitant medication and measurements of vital signs, weight and height, and laboratory tests. Clinically significant abnormalities observed during the physical examination are recorded as either medical history or AEs, as appropriate.

Safety assessments are to be performed as specified in the Schedule of Assessments (Table 1). On dosing days and as applicable, assessments of vital signs, weight/height, physical examination, and clinical laboratory assessments are to be completed before study drug administration.

Adverse event assessments are detailed under Section 6.5.5.

### 6.5.1. Vital Signs

Vital signs will be measured as specified in the Schedule of Assessments (Table 1) and include blood pressure, heart rate, body temperature, and respiratory rate. Vital signs will be measured predose, when applicable. When vital signs and blood sample collection occur at the same time, vital signs should be performed before blood samples are drawn, where possible. Vital signs should be measured predose in the seated or supine position, after the patient has rested comfortably for approximately 5 minutes. Blood pressure should be taken using the same arm when feasible. Body temperature in degrees Celsius will be obtained via oral, tympanic, or axillary methods. Heart rate will be counted for a full minute and recorded in beats per minute, and respiration rate will be counted for a full minute and recorded in breaths per minute.

Additional vital sign assessments, as medically indicated, may be added at the discretion of the Investigator.

Vital signs results will be recorded in the eCRF.

## 6.5.2. Height and Weight

Height will be measured in centimeters. Body weight will be measured in kilograms. Height and body weight measurements will be collected as specified in the Schedule of Assessments (Table 1) and will be recorded in the eCRF.

### 6.5.3. Physical Examination

Full and symptom-directed physical examinations will be conducted according to the Schedule of Assessments (Table 1); if a physical examination is scheduled for a dosing visit, it should be conducted prior to dosing. Full physical examinations will include the examination of the following: general appearance; head, eyes, ears, nose and throat; respiratory, cardiovascular, gastrointestinal, musculoskeletal, and dermatological systems; thyroid; lymph nodes; and neurological status. If a visit is conducted offsite (eg, home), a body system assessment may be performed in lieu of a physical examination.

Symptom-directed physical examinations will be guided by evaluation of ongoing symptoms, changes in symptoms, or the onset of new symptoms, since the last visit. If there are no ongoing symptoms, changes in symptoms, or new symptoms, then a symptom-directed physical examination is not required.

Clinically significant abnormalities observed during the physical examination are recorded on the medical history eCRF (if observed during screening) or the AE eCRF (if observed at any post-screening visit).

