Single 24-hour urine collection	Collect within 14 days prior to dosing (M3) or visit (M4, M5, M6); repeat if invalid. See Table 4			х	х	Х	Х			
Blood sample for PD analyses	Section 6.3	X	X	X			X	X	X	
Clinical laboratory assessments	Section 6.5.4	X	X	X			X	X	X	X
Antidrug antibody sample	Section 6.5.4.1		X	X			X	X	X	X
Urine pregnancy test (for WOCBP) c	May be performed more frequently where required per local requirements, or if pregnancy is suspected. See Section 6.5.4.2		х	X				Х		
Symptom-directed physical examination	Section 6.5.3		X	X				X		X
Prior and concomitant medications	Section 5.4		Continuous							

Table 1: Schedule of Assessments

			1	5 Monti Treati	h Doub nent Pe		I			
		Screening	Pri	mary A	nalysis l	Period		Treat Exter Per	nsion	Safety
Study Visit			Baseline	М3	M4	MS	М6	ЕОТ М9	EOS/ ET M15	Follow-up (Patients who D/C Treatment Early)
Study Day (±Visit Window)	Notes	-60 to -1	Day 1	85 (±14)	113 (±7)	(41 (±7)	169 (±14)	253 (±28)	421 (±28)	3 and 6 months post last dose (±28)
Clinical kidney stone events	Section 6.2.2				C	ontinuo	us			
Review/record adverse events	Section 6.5.5				C	ontinuo	us			
Healthcare utilization	Section 6.6				C	ontinuo	us			
Randomization	Window: 1 business day prior to Day 1 for study drug preparation		X							
Blood samples for PK analyses	Table 2; Section 6.4		X							
Study drug administration	Section 5.2.2		X	X				X		
Optional low-dose kidney- protocol CT scan d	Section 6.2.2.2		X (-3 days window)			1 64			X	

Abbreviations: CT=computed tomography; D/C=discontinue; ET=early termination; EOS=end of study; EOT=end of treatment; M=month; PD=pharmacodynamic; PK=pharmacokinetic; WOCBP=women of child-bearing potential Notes:

- When scheduled at the same time points, assessments of vital signs should be performed before physical examinations and blood sample collections, where feasible.
- Patients who discontinue study drug dosing for any reason will be encouraged to remain on the study to complete the remaining assessments so that their experience is captured in the final analyses (refer to Section 4.3.1).

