- White columns indicate visits to the clinical study center; gray-shaded columns indicate study visits that may be conducted by a home healthcare professional, where applicable country and local regulations and infrastructure allow (at the discretion and with oversight of the Investigator, based on safety and tolerability), provided (for dosing visits) that the patient has tolerated a dose of lumasiran administered in the clinic. If a visit is conducted offsite, a body system assessment may be performed in lieu of a symptom-directed physical examination.
- In situations where a study visit is unable to be completed (either at the site or offsite by a healthcare professional), the Investigator (or delegate) will verbally contact the patient within the study visit window to assess concomitant medications, kidney stone events, and adverse events.

Footnotes:

- a All assessments are required to be performed prior to dosing at dosing visits, except for the PK 2-hour postdose sample collection and optional CT scan.
- b Inclusion/exclusion criteria should be verified prior to randomization. Laboratory assessments conducted to confirm study eligibility will not be repeated unless the time between screening and randomization exceeds 4 weeks.
- c Pregnancy test results must be known prior to dosing, if applicable.
- d Patients who elect to participate in optional CT scans will be requested to complete CT scans at both baseline (may be performed up to 3 days prior to Day 1), and at Month 15. The CT scans may be performed after dosing, if required.

Alnylam Pharmaceuticals Confidential 12

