# 3. INVESTIGATIONAL PLAN

# 3.1. Summary of Study Design

This is a randomized, placebo-controlled, double-blind, multi-center, multinational, Phase 2 study to evaluate the efficacy, safety, PD, and PK of lumasiran administered SC in patients with recurrent calcium oxalate kidney stone disease and elevated urinary oxalate levels (Figure 1).

The study will consist of up to 2 months of screening and 15 months of double-blind treatment (a 6-month Primary Analysis Period followed by a 9-month Treatment Extension Period). Patients will be screened from Day -60 to Day -1 to determine eligibility. During screening, patients will provide at least two 24-hour urine collections to establish baseline urinary oxalate levels. Consented patients meeting all eligibility criteria will be randomized 1:1:1 to receive study drug: lumasiran 567 mg, lumasiran 284 mg, or placebo. Stratification will be performed at randomization according to baseline urinary oxalate level ( $\leq 1.25 \times ULN \text{ vs} > 1.25 \times ULN$ ) from the mean of the first 2 valid 24-hour urine collections and the number of historical kidney stone events in the 12 months prior to screening ( $\leq 1 \text{ vs} > 1$ ), as discussed in Section 3.4.

During the 6-month Primary Analysis Period, patients will be dosed on Day 1 (baseline) and at Month 3. During the Treatment Extension Period, one additional dose will be administered at Month 9; an end of study (EOS) visit will take place at Month 15. Study drug will be administered SC as specified in Section 5.2.2. Patients will be assessed for efficacy, safety, PD, and PK according to the Schedule of Assessments (Table 1 and Table 2). Efficacy assessments will include evaluation of urinary oxalate excretion, urinary calcium oxalate supersaturation, and kidney stone events (including clinical events and radiologic events with optional low-dose kidney-protocol CT). Safety assessments will include collection of AEs, clinical laboratory tests, vital sign assessments, physical examinations, and concomitant medications.

Patients who discontinue study drug early will be asked to return for follow-up visits as described in Section 4.3.1.

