#### **Recording Adverse Events**

The Investigator is responsible for recording non-serious AEs that are observed or reported by the patient after administration of the first dose of study drug regardless of their relationship to study drug through the EOS. Non-serious AEs will be followed until the EOS. Events occurring after signing of the ICF and before study drug administration will be captured as medical history (see Section 6.1), while AEs that occur after study drug administration, and baseline events that worsen after study drug administration, must be recorded as AEs.

The Investigator is responsible for recording SAEs that are observed or reported by the patient after the time when the informed consent is signed regardless of their relationship to study drug through the EOS. Serious AEs will be followed until satisfactory resolution, until baseline level is reached, or until the SAE is considered by the Investigator to be chronic or the patient is stable, as appropriate.

All AEs must be recorded in the source records for the clinical study center and in the eCRF for the patient, whether or not they are considered to be drug-related. Each AE must be described in detail: onset time and date, description of event, severity, relationship to study drug, action taken, and outcome (including time and date of resolution, if applicable).

For SAEs, record the event(s) in the eCRF and, as applicable, the SAE form.

For AEs that are considered AEs of clinical interest (Section 6.5.5.1), the supplemental AEs of Clinical Interest eCRF should be completed. Additional clinical and laboratory information may be collected. Refer to eCRF completion guidelines for details on reporting events in the supplemental AEs of Clinical Interest eCRF.

For all ISRs, the Investigator, or delegate, should submit an Injection Site Reaction Signs or Symptoms eCRF, recording additional information regarding each injection site reaction that is entered on the AE eCRF (eg, symptom(s), injection site location, follow-up actions taken, etc.).

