5.11.1. Adverse Events

Adverse events (AEs) will be classified by the MedDRA coding system (version 24.1) and displayed in tables and data listings using SOC and PT.

Treatment-emergent AEs (TEAEs) will be summarized, where TEAE is defined as any AE occurring or worsening on or after the first dose of study drug and through 168 days after the last dose or any study drug-related AE. Because any worsening AE is reported as a new AE with higher severity, programmatical comparison of severity is not needed for the classification of TEAE. For missing or partial dates for AEs, the imputation of start and end date can be found in Section 7.3. Events with a fully or partially missing onset date will be assumed to be treatment emergent unless it can be unequivocally determined (from the partial onset date and/or a partial or complete stop date) that the event occurred prior to the first dose of study drug. All TEAEs hereafter will be referred to as AEs in this document.

AEs will be summarized by the numbers and percentages of patients reporting a given AE. An overall table of TEAEs will include, but not limited to:

- At least 1 AE
- At least 1 drug related AE
- At least 1 severe AE
- At least 1 drug related severe AE
- At least 1 Serious Adverse Event (SAE)
- At least 1 drug related SAE
- At least 1 AE leading to treatment discontinuation
- At least 1 AE leading to drug interruption
- At least 1 drug related AE leading to treatment discontinuation
- At least 1 AE leading to study withdrawal
- At least 1 drug related AE leading to study withdrawal
- Death (based on SAE CRFs)

Tabulations by SOC and PT will be produced for the following:

- AEs,
- Treatment-related AEs,
- AEs by maximum severity,
- Treatment-related AEs by maximum severity,
- Severe AEs,
- Treatment-emergent SAEs,
- AEs leading to treatment discontinuation.

Tabulations by PT in decreasing order in frequency within each treatment arm will be produced for the following:

- AEs
- Treatment-related AEs
- SAEs

AEs and AEs related to treatment will also be summarized by severity. A patient contributes only once to the count for a given AE (overall, by SOC, by preferred term). Patients who report multiple occurrences of the same AE (preferred term) will be classified according to the most severe occurrence. An AE with missing severity will be assumed to be severe. An AE with missing study drug relatedness will be assumed to be related.

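### Protocol 6.5.3 and 6.5.5.2 disagree on whether a clinically significant abnormality first seen at the pre-dose Day 1 examination is an adverse event or medical history

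*Protocol*

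**What the plan says.** Protocol 6.5.3 divides examination findings by visit. It covers clinically significant abnormalities, which are "recorded on the medical history eCRF (if observed during screening) or the AE eCRF (if observed at any post-screening visit"). Protocol 3.1 fixes the screening period: "Patients will be screened from Day -60 to Day -1 to determine eligibility". Day 1 is therefore a post-screening visit.

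Table 1 has a row headed "Symptom-directed physical examination", marked at Day 1, Month 3, Month 9 and the safety follow-up. Footnote a to that table says "All assessments are required to be performed prior to dosing at dosing visits", with exceptions only for the 2-hour PK sample and the optional CT scan. Section 6.5.3 repeats the pre-dose requirement for examinations. It also says that without ongoing, changed or new symptoms "then a symptom-directed physical examination is not required".

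Protocol 6.5.5.2 divides by dosing instead: "Events occurring after signing of the ICF and before study drug administration will be captured as medical history". It limits non-serious AEs to events after study drug and to baseline events that worsen after it. SAEs are recorded from consent. Section 6.1 keeps medical history open for updating until dosing, and Table 1 schedules a medical-history entry on Day 1. Section 6.5 says only that examination abnormalities go to one place or the other as appropriate.

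In the SAP, 5.11.1 says "TEAE is defined as any AE occurring or worsening on or after the first dose of study drug" (through 168 days after the last dose), and adds any event related to study drug.

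**The concern.** A clinically significant abnormality found on Day 1 before the injection is an AE under 6.5.3 and medical history under 6.5.5.2. Section 6.5.3 is the one that deals directly with examination findings, so a site could reasonably follow it. Two sites could then record the same finding differently.

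This matters because Protocol 7.2.8 makes the frequency of treatment-emergent AEs the primary safety parameter. A condition that existed before any exposure could enter that count, and it would drop out of the medical-history summary in SAP 5.3. SAP 5.11.1 does not say whether Day 1 events are compared with the first dose by date or by clock time, so the analysis does not reliably undo the recording error.

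**Working it through.** No design calculation bears on this and the plan states no figure to reproduce. The check follows one clinically significant Day 1 pre-dose finding through both documents.

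**Step 1: where it is recorded**

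- Protocol 6.5.5.2 with 6.1: before study drug, so medical history. It never reaches the AE data.
- Protocol 6.5.3: screening ended on Day -1, so the AE form.
- Month 3 and Month 9: these examinations precede that visit's dose but follow the first dose, so both rules treat a new finding as an AE. The conflict is confined to Day 1.

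**Step 2: what the SAP does with it once it is on the AE form**

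| Entry on the AE form | SAP rule | Treatment-emergent? |
|---|---|---|
| Full onset date before Day 1, relatedness no | 5.11.1 definition | No; also absent from the 5.3 summary |
| Onset Day 1, compared by date | 5.11.1 definition | Yes |
| Onset Day 1, compared by recorded time | 5.11.1 definition | No |
| Onset day missing, month is that of first dose | 7.3 imputes the first dosing day | Yes, unless a stop date shows it was earlier |
| Onset year missing | 5.11.1 presumption and 7.3 | Yes, unless a stop date shows it was earlier |
| Relatedness missing | 5.11.1 assumes related, which meets the drug-related limb | Yes, whatever the onset |

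The second and third rows differ only in whether clock time is used. SAP 4.4 does specify both date and time of first dose for the laboratory and vital-sign baselines. SAP 5.11.1 has no equivalent, although Protocol 6.5.5.2 requires AE onset time as well as date.

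**Step 3: size**

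- Planned arm size is 40 (Protocol 7.1). One misclassified patient changes the arm's overall proportion with any AE by 1/40 = 2.5 percentage points if that patient has no other AE, and by 0 otherwise, because SAP 5.11.1 counts each patient once. In a preferred-term row, the same 1/40 applies unless the patient already has that term.
- The documents give no rate of such findings. Purely as an assumption, 1% to 5% of 120 patients is 1.2 to 6 patients across the trial, or 0.4 to 2 per arm. This is a ceiling for the assumed rate: it supposes that every site follows 6.5.3 and that every entry becomes treatment-emergent.
- If a share m of patients is wrongly counted in every arm, independently of true AEs, a true proportion p becomes p + m(1 − p), and the difference between two arms is multiplied by (1 − m). Illustration with m = 0.05: 60% becomes 0.60 + 0.05 × 0.40 = 62.0%, and 50% becomes 0.50 + 0.05 × 0.50 = 52.5%. The difference falls from 10 to 9.5 points.

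**The case against.** The strongest reply is that 6.5.5.2 governs AE recording and is explicit, that 6.1 and the Day 1 medical-history entry agree with it, and that 6.5 leaves room for it. On that view 6.5.3 contains one loose sentence and most sites will do the right thing. The first part stands: a reader might infer that the protocol puts pre-dose conditions on the AE form as a matter of course, and it does not. It gives two opposite instructions.

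Nor does 6.5.3 reach every finding. It covers clinically significant abnormalities only, and the Day 1 examination is symptom-directed and can be omitted when there are no symptoms.

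A reader might also infer that any such entry becomes treatment-emergent. That is not supported either. The SAP wording refers to the first dose, not the day of the first dose, so a time-based reading is open. The symptoms prompting the examination may have begun before Day 1, and a full earlier onset with relatedness recorded as no is excluded.

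Finally, safety is summarized descriptively, so no test is at risk, and the AE entry still appears in the patient listings, so the information is not lost. Those points limit the consequence. They do not remove the contradiction, and they do not settle how a Day 1 onset is compared with the dose.

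**Conclusion.** The two protocol sections conflict for one specific, scheduled situation: a clinically significant abnormality first seen at the pre-dose Day 1 examination. Whether it then inflates the treatment-emergent count depends on the site following 6.5.3 and on one of three further conditions: a date-only comparison of a Day 1 onset, a partial or missing onset imputed to the first dosing day, or missing relatedness.

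The effect is probably small. Its frequency cannot be estimated from the documents, and the 1% to 5% used above is an assumption without a source. Under equal misclassification across arms, counts rise slightly in all arms and the contrast shrinks by the factor (1 − m). A claim of material dilution of the lumasiran–placebo difference is not supported. This is a minor inconsistency in data recording, worth correcting because it touches the primary safety parameter and costs almost nothing to remove.

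**What to change.** 1. **Protocol 6.5.3.** Replace the split by visit with a split at the first dose of study drug: medical history if the abnormality was present before the first dose, AE if it is new or has worsened after it. State in the same sentence that SAEs are still recorded from informed consent as 6.5.5.2 requires. Without that exception the new wording would create a fresh conflict for serious pre-dose findings.
2. **SAP 5.11.1.** State that events with onset on Day 1 are classified by onset time against the time of first dose where both are recorded, and say what applies when a time is missing.

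The cost is one sentence in each document, plus matching text in any eCRF completion guidance. No new data are needed: AE onset time is already required by 6.5.5.2, and SAP 4.4 already relies on the time of first dose.
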